# Hyperostosis (PTs) -

Administration site pain	Injection sit	e inflammation	
Hyperostosis (PTs) -		Maix	ouz ille
Acquired foramen magnum steno	sis	Foramen magnum stenosis	
Acral overgrowth		High turnover osteopathy	
Bone formation increased		Intracranial pressure increas	ed
Cervical spinal stenosis		Lumbar spinal stenosis	
Diffuse idiopathic skeletal hypero	ostosis	Macrogenia	
Enostosis		Melorheostosis	
Exostosis	(b)	Periostosis	
Exostosis of external ear canal	), X	Vertebral foraminal stenosis	3
Exostosis of jaw	-0-	Vertebral lateral recess stend	osis
Extraskeletal ossification	60 7		

# Osteoarthritis (PTs) -

Ankle arthroplasty	Nodal osteoarthritis
Arthritis	Osteoarthritis
Arthropathy	Osteoarthropathy
Exostosis	Polyarthritis
Facet joint syndrome	Rapidly progressive osteoarthritis
Hip arthroplasty	Shoulder arthroplasty
Interspinous osteoarthritis	Spinal osteoarthritis
Joint arthroplasty	Vertebral osteophyte
Knee arthroplasty	

Confidential

#### 13.6 **Adverse Event of Special Interest (PDILI)**

AESI are defined by the PTs for the PDILI SMQ.	•
Acquired antithrombin III deficiency	Jariations thereof.
Acquired factor IX deficiency	
Acquired factor V deficiency	.10
Acquired factor VIII deficiency	
Acquired factor XI deficiency	,,0,
Acquired hepatocerebral degeneration	
Acquired protein S deficiency	
Acute graft versus host disease in liver	
Acute hepatic failure	
Acute on chronic liver failure	10, 110
Acute yellow liver atrophy	all s
Alanine aminotransferase abnormal	100 M
Alanine aminotransferase achormat	11. 110
Allergic hepatitis	7 : 0
Alloimmune hepatitis	
Ammonia abnormal	7
Ammonia increased	
Anti factor X activity abnormal	
Anti factor X activity decreased	
Anti factor X activity increased	
Antithrombin III decreased	
Ascites	
Aspartate aminotransferase abnormal	
Aspartate aminotransferase increased	
AST/ALT ratio abnormal	
Asterixis	
Autoimmune hepatitis	
Bacterascites A	
Bile output abnormal	
Bile output decreased	
Biliary ascites	
Biliary cirrhosis	
Bihary fibrosis	
Bilirubin conjugated abnormal	
Bilirubin conjugated increased	
Bilirubin excretion disorder	
Bilirubin urine present	
Biopsy liver abnormal	
Blood bilirubin abnormal	

Confidential Page 56 of 89

Blood bilirubin increased	
Blood bilirubin unconjugated increased	
Blood fibrinogen abnormal	
Blood fibrinogen decreased	
Blood thrombin abnormal	;(O)
Blood thrombin decreased	
Blood thromboplastin abnormal	
Blood thromboplastin decreased	*horiZation
Bromosulphthalein test abnormal	
Cardiohepatic syndrome	
Child-Pugh-Turcotte score abnormal	0,00
Child-Pugh-Turcotte score increased	11/20 2/0
Cholaemia	
Cholestasis	The silver
Cholestatic liver injury	20, 72
Cholestatic pruritus	. (1) ::(0)
Chronic graft versus host disease in liver	A . All
Chronic hepatic failure	Augitations thereof.
Chronic hepatitis	7,0
Coagulation factor decreased	
Coagulation factor IX level abnormal	
Coagulation factor IX level decreased	
Coagulation factor V level abnormal	
Coagulation factor V level decreased	
Coagulation factor VII level abnormal	
Coagulation factor VII level decreased	
Coagulation factor X level abnormal	
Coagulation factor X level decreased	
Coma hepatic	
Computerised tomogram liver abnormal	
Congestive hepatopathy	
Cryptogenic cirrhosis	
Diabetic hepatopathy	
Drug-induced liver injury	
Duodenal varices	
Flood syndrome	
Foetor hepaticus	
Galactose elimination capacity test abnormal	
Galactose elimination capacity test decreased	
Gallbladder varices	
Gamma-glutamyltransferase abnormal	
Gamma-glutamyltransferase increased	
Gastric variceal injection	

Confidential Page 57 of 89

Gastric variceal ligation		
Gastric varices		
Gastric varices haemorrhage		
Gastrooesophageal variceal haemorrhage prophylaxis		
Graft versus host disease in liver		40
Guanase increased	40	V)
Hepaplastin abnormal	\J	,
Hepaplastin decreased	0	
Hepatectomy	Jailations thereof.	
Hepatic artery flow decreased	2) × .	
Hepatic atrophy	0,00	
Hepatic calcification	4/100	
Hepatic cirrhosis		
Hepatic cytolysis	1	
Hepatic encephalopathy	~9, ~2	
Hepatic encephalopathy prophylaxis	1, 4, 2,0,	
Hepatic enzyme abnormal	4 : 22	
Hepatic enzyme decreased		
Hepatic enzyme increased	7.0.	
Hepatic failure		
Hepatic fibrosis		
Hepatic function abnormal		
Hepatic hydrothorax		
Hepatic hypertrophy		
Hepatic hypoperfusion		
Hepatic infiltration eosinophilic		
Hepatic lesion		
Hepatic mass		
Hepatic necrosis		
Hepatic pain		
Hepatic sequestration		
Hepatic steato-fibrosis		
Hepatic steatosis		
Hepatic vascular resistance increased		
Hepatic venous pressure gradient abnormal		
Hepatic venous pressure gradient increased		
Hepatitis		
Hepatitis acute		
Hepatitis cholestatic		
Hepatitis chronic active		
Hepatitis chronic persistent		
Hepatitis fulminant		
Hepatitis toxic		

Confidential Page 58 of 89

Hepatobiliary disease		
Hepatobiliary scan abnormal		
Hepatocellular foamy cell syndrome		
Hepatocellular injury		~
Hepatomegaly		.:.0
Hepatopulmonary syndrome		All
Hepatorenal failure	: 1	
Hepatorenal syndrome		
Hepatosplenomegaly	Jailations thereof.	
Hepatotoxicity	201 8	
Hyperammonaemia	0,00	
Hyperbilirubinaemia	11/09 (0)	
Hypercholia	Sill, No.	
Hyperfibrinolysis	14. 11.	
Hypertransaminasaemia		
Hypocoagulable state	(0)	
Hypofibrinogenaemia	A . All	
Hypoprothrombinaemia		
Hypothrombinaemia	7,0	
Hypothromboplastinaemia		
Icterus index increased		
Immune-mediated cholangitis		
Immune-mediated hepatic disorder		
Immune-mediated hepatitis		
International normalised ratio abnormal		
International normalised ratio increased		
Intestinal varices		
Intestinal varices haemorrhage		
Ischaemic hepatitis		
Jaundice		
Jaundice cholestatic		
Jaundice hepatocellular		
Kayser-Fleischer ring		
Liver dialysis		
Liver disorder		
Liver function test abnormal		
Liver function test decreased		
Liver function test increased		
Liver induration		
Liver injury		
Liver operation		
Liver palpable		
Liver scan abnormal		

Confidential Page 59 of 89

Liver tenderness	
Liver transplant	$\dashv$
Lupoid hepatic cirrhosis	$\dashv$
Lupus hepatitis	-
Magnetic resonance imaging hepatobiliary abnormal	
Magnetic resonance proton density fat fraction measurement	*HOilZation
Mitochondrial aspartate aminotransferase increased	
Mixed liver injury	
Molar ratio of total branched-chain amino acid to tyrosine	
Nodular regenerative hyperplasia	
Nonalcoholic fatty liver disease	Mariations thereof.
Non-alcoholic steatohepatitis	
Non-cirrhotic portal hypertension	- 100 100
Ocular icterus	- All Sti
Oedema due to hepatic disease	
Oesophageal varices haemorrhage	1,11,110,
Parenteral nutrition associated liver disease	d in the second
Perihepatic discomfort	
Peripancreatic varices	120
Portal hypertension	
Portal hypertensive colopathy	_
Portal hypertensive enteropathy	
Portal hypertensive gastropathy	
Portal vein cavernous transformation	
Portal vein dilatation	
Portopulmonary hypertension	
Primary biliary cholangitis	
Protein C decreased	
Protein S abnormal	
Protein S decreased	
Prothrombin level abnormal	
Prothrombin level decreased	
Prothrombin time abnormal	
Prothrombin time prolonged	
Prothrombin time ratio abnormal	
Prothrombin time ratio increased	
Radiation hepatitis	
Regenerative siderotic hepatic nodule	
Renal and liver transplant	
Retrograde portal vein flow	
Reye's syndrome	
Reynold's syndrome	
	_

Confidential Page 60 of 89

Splenic varices	
Splenic varices haemorrhage	
Spontaneous bacterial peritonitis	
Steatohepatitis	^
Subacute hepatic failure	:12ilon
Sugiura procedure	
Thrombin time abnormal	
Thrombin time prolonged	
Total bile acids increased	A Mariations the reof.
Transaminases abnormal	all &
Transaminases increased	0.00
Ultrasound liver abnormal	
Urine bilirubin increased	
Varices oesophageal	The sill.
Varicose veins of abdominal wall	20, 20
White nipple sign	(0): (1)
X-ray hepatobiliary abnormal	4 . 2
13.7 Lipid-Type of Adverse Event	7.0.
Lipid-type AEs are defined by the PTs for the dyslipidaemia SMo	Q.
Acquired lipoatrophic diabetes	
Acquired mixed hyperlipidaemia	

#### **Lipid-Type of Adverse Event** 13.7

Acquired mixed hyperlipidaemia Apolipoprotein B/Apolipoprotein A-1 ratio increased Autoimmune hyperlipidaemia Blood cholesterol abnormal Blood cholesterol decreased Blood cholesterol esterase increased Blood cholesterol increased Blood triglycerides abnormal Blood triglycerides decreased
Autoimmune hyperlipidaemia  Blood cholesterol abnormal  Blood cholesterol decreased  Blood cholesterol esterase increased  Blood cholesterol increased  Blood triglycerides abnormal
Blood cholesterol abnormal Blood cholesterol decreased Blood cholesterol esterase increased Blood cholesterol increased Blood triglycerides abnormal
Blood cholesterol decreased Blood cholesterol esterase increased Blood cholesterol increased Blood triglycerides abnormal
Blood cholesterol esterase increased Blood cholesterol increased Blood triglycerides abnormal
Blood cholesterol increased Blood triglycerides abnormal
Blood triglycerides abnormal
Blood triglycerides decreased
Blood trigiyeendes decreased
Blood triglycerides increased
Diabetic dyslipidaemia
Dyslipidaemia
Familial high density lipoprotein deficiency
Familial hypertriglyceridaemia
Fat overload syndrome
High density lipoprotein abnormal
High density lipoprotein decreased
High density lipoprotein increased
Hypercholesterolaemia

Confidential Page 61 of 89

Hyperlipidaemia	
Hypertriglyceridaemia	
Hypo HDL cholesterolaemia	
Hypotriglyceridaemia	ithorization.
Intermediate density lipoprotein decreased	,,0)
Intermediate density lipoprotein increased	
LDL/HDL ratio decreased	
LDL/HDL ratio increased	
Lecithin-cholesterol acyltransferase deficiency	
Lipid metabolism disorder	
Lipids abnormal	1 0 00
Lipids decreased	
Lipids increased	
Lipoprotein (a) abnormal	
Lipoprotein (a) decreased	D
Lipoprotein (a) increased	
Lipoprotein abnormal	ations thereof.
Lipoprotein increased	
Lipoprotein metabolism disorder	1
Low density lipoprotein abnormal	1
Low density lipoprotein decreased	1
Low density lipoprotein increased	]
Metabolic syndrome	1
Non-high-density lipoprotein cholesterol decreased	1
Non-high-density lipoprotein cholesterol increased	1
Primary hypercholesterolaemia	1
Remnant hyperlipidaemia	1
Remnant-like lipoprotein particles increased	]
Total cholesterol/HDL ratio abnormal	
Total cholesterol/HDL ratio decreased	1
Total cholesterol/HDL ratio increased	1
Type I hyperlipidaemia	]
Type II hyperlipidaemia	1
Type IIa hyperlipidaemia	1
Type IIb hyperlipidaemia	
Type III hyperlipidaemia	
Type IV hyperlipidaemia	
Type V hyperlipidaemia	
Very low density lipoprotein abnormal	
Very low density lipoprotein decreased	
Very low density lipoprotein increased	

13.8

### Immunogenicity Analysis

### ADA analysis: subject classification, incidence, time of onset and time profiles

Anti-romosozumab antibodies (ADA) will be measured using a three-tiered assay approach: screening assay, confirmatory assay and titration assay.

Romosozumab

Samples will first be evaluated in the screening assay using a false positivity rate of 5% (reported as 'negative screen' or 'positive screen'), followed by analysis of screened positive samples in the confirmatory assay (which is a drug depletion assay) to confirm the true positivity of the samples (reported as 'negative immunodepletion' or 'positive immunodepletion'). Samples that are confirmed as positive will be evaluated in a titration assay to quantify the ADA level and will be reported as titer (reciprocal dilution factor including minimum required dilution).

Confirmed positive ADA samples will be subjected to an in vitro neutralizing antibody (NAb) assay.

Placebo samples will not be analysed for ADA. The summaries and figures will be done for the following analyses:

- Month 1-6 of romosozumab/romosozumab treatment group at 6-month analysis
- Month 1-12 of romosozumab/romosozumab treatment group at final analysis
- Month 1-6 of romosozumab/romosozumab group pooled with month 6-12 of placebo/romosozumab treatment group at final analysis

The ADA status should be determined for each visit where samples were taken for ADA analysis.

- Sample values that are either 'negative screen' or 'positive screen' and 'negative immunodepletion' will be defined as **ADA negative**
- Sample values that are 'positive screen' and 'positive immunodepletion' will be defined as **ADA positive**

In addition, the anti-drug antibody status will be further classified based on subject levels as outlined below. This classification should be done for entire study duration (i.e. the treatment period including SFU sampling time point).

- 1. **Pre ADA negative treatment induced ADA negative**: Includes study participants who are negative at Baseline and antibody negative at all sampling points post treatment. This group also includes study participants who have a missing pre-treatment sample (either missing or insufficient volume) at Baseline with all ADA post-treatment samples negative.
- 2. **Pre ADA negative treatment induced ADA positive**: Includes study participants who are negative at Baseline and antibody positive at any sampling point post treatment. This group also includes study participants who have a missing pre-treatment sample (either missing or insufficient volume) at Baseline with one or more ADA positive post-treatment samples.

Confidential Page 63 of 89

- 3. **Pre ADA positive treatment reduced ADA**: Includes study participants who are positive at Baseline, and antibody negative at all sampling points post treatment
- 4. **Pre ADA positive treatment unaffected ADA**: Includes study participants who are positive at Baseline and are positive at any sampling point post treatment with titer values of the same magnitude as Baseline (ie, less than a predefined fold difference increase from the Baseline value, i.e. the minimum significant ratio (MSR) determined during assay validation).
- 5. Pre ADA positive treatment boosted ADA positive: Includes study participants who are positive at Baseline and are positive at any sampling point post treatment with increased titer values compared to Baseline (greater than a predefined fold difference increase from Baseline value, i.e. the minimum significant ratio (MSR) determined during assay validation).
- 6. **Inconclusive**: Includes study participants who have a positive or negative pre-treatment sample and some post-treatment samples are missing, while other post-treatment samples are ADA negative.

The fold difference increase (i.e. the minimum significant ratio (MSR) determined during assay validation) from baseline needed to consider a titer value reported post-treatment to be above the assay variation will be noted in the relevant tables, listings and figures.

Based on the overall ADA subject classification above, the following will be determined and presented:

- o Total prevalence of pre-Ab: n/N% number of subjects that are preADA positive.
- Total incidence of treatment-emergent ADA positive : n/N % number of subjects in category 2 and category 5

In the case that a sample is collected one or more days following the scheduled visit date in which the drug was administered, the ADA results for that sample will be associated with the scheduled visit and summarized accordingly. Such samples will also be considered when ADA results are summarized over a given study period.

The following summaries, figures and listings will be produced and will be presented using the SS.

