7 STUDY TREATMENT

7.1 Description of investigational medicinal product

For this study, romosozumab and placebo are considered IMP.

Subjects will be administered either romosozumab or placebo in a blinded manner for 6 months after which time, all subjects will receive active treatment (romosozumab) in an OL manner for 6 months.

Romosozumab will be supplied as a sterile, clear to opalescent, colorless to light yellow, preservative-free solution for sc injection in a single-use prefilled syringe (PFS). Each PFS contains 90mg/mL of romosozumab in 55mM acetate and 13mM calcium containing 6.0% w/v sucrose and 0.006% w/v polysorbate 20 at pH 5.2, with a deliverable volume of 1.17mL (105mg romosozumab solution for injection).

Placebo is supplied in a 1.17-mL PFS identical in appearance to romosozumab. Placebo will be stored and packaged the same as romosozumab.

Details of the IMP are provided in the IMP Handling Manual.

Subjects will be required to take daily calcium and vitamin D supplementation during the study; however, these protocol-required products are not considered IMP. Further information on the calcium and vitamin D supplementation is provided in Section 7.8.1.1.

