11.7.5 Antibodies to romosozumab

Blood samples for antiromosozumab antibody testing will be collected from subjects at the time points indicated in Table 5–1. However, only samples from subjects who receive romosozumab will be analyzed for antiromosozumab binding antibodies.

A fully validated bioanalytical method will be utilized to determine antibodies to romosozumab. Detailed information on sample analysis will be provided in a separate bioanalytical report.

The investigator will be notified of any positive neutralizing antibody results to romosozumab detected at the EOS Visit or ET Visit. Subjects who test positive for neutralizing antibodies to romosozumab at the EOS Visit or ET Visit will be asked to return for additional follow-up testing. This testing should occur approximately every 3 months starting from when the site has been notified of the positive result, until: (1) neutralizing antibodies are no longer detectable or (2) the subject has been followed for a period of at least 1 year (±4 weeks) after IMP administration. All follow-up results both positive and negative will be communicated to the site. More frequent testing (eg, QM) or testing over a longer period may be requested in the event of safety-related concerns.

Subjects who test positive for binding, non-neutralizing antibodies and have clinical sequelae that are considered potentially related to an antiromosozumab antibody response may also be asked to return for additional follow-up testing.

Blood samples for antibody determination will be processed and analyzed by the bioanalytical laboratory.

Methods for collecting, processing, storing, and shipping of the samples are presented in further detail in the bioanalytical laboratory manual.

No notifications of a positive antibody status will be sent to the investigator before the EOS Visit or ET Visit to avoid any potential unblinding during the Double-Blind Placebo-Controlled Period and to minimize any bias being introduced during the OL Treatment Period, once the investigator is unblinded to individual treatment assignments.

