# 3.3 Definition of Baseline values

A Baseline value for a subject is defined as the latest measurement for that subject up to and including the day of administration of first IMP, unless otherwise stated. If there is evidence that measurements taken on the same day as administration of first study medication were actually taken after this administration, then only values strictly prior to that date should be considered for that subject for baseline. If multiple measurements within the baseline period were done, the record that is the closest to and prior to or on the date of first IMP administration will be considered as the Baseline value. If a Baseline measurement is missing or not collected, and a Screening value (within 35 days prior to day 1) is available, the Screening value will be utilized as Baseline instead.

For computation of change from Baseline BMD of lumbar spine endpoint, Baseline will be identified as the average number of values (averaging is dedicated to the duplicate BMD values taken on the same day) obtained prior to the first dose of IMP (assuming that any observation on the same day as the first dose is prior to dosing, unless evidence stated). For computation of change from Baseline BMD of femoral neck and total hip, also other change from Baseline endpoints, the Baseline will be identified as the last observation prior to the first dose of IMP (assuming that any observation on the same day as the first dose is prior to dosing, unless evidence stated). The randomization date will be used as reference for subjects who did not receive any dose of IMP but who had non-missing observations on study.

Confidential Page 21 of 89

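### SAP 13.8 names no pre-romosozumab ADA reference for subjects who switch from placebo, so on its plain reading persisting pre-existing reactivity in that arm would count as treatment-emergent

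*SAP*

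**What the plan says.** **Which samples are assayed.** SAP 13.8 states "Placebo samples will not be analysed for ADA". Protocol 11.7.5 selects differently: "only samples from subjects who receive romosozumab will be analyzed for antiromosozumab binding antibodies". The SAP sentence is about samples; the protocol sentence is about subjects.

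**Who enters the summaries.** One of the three ADA analyses in SAP 13.8 is described as "Month 1-6 of romosozumab/romosozumab group pooled with month 6-12 of" the placebo/romosozumab group, at the final analysis. SAP 10.4.5 also tabulates antibody incidence to Month 12 for both groups.

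**How subjects are classed.** Category 2 is for subjects negative at Baseline and positive at some later point. Of subjects without a pre-treatment result, the SAP says: "This group also includes study participants who have a missing pre-treatment sample (either missing or insufficient volume) at Baseline with one or more" positive samples afterwards. The summary measure "Total incidence of treatment-emergent ADA positive" is defined from the "number of subjects in category 2 and category 5".

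**What Baseline means.** SAP 3.3 defines it as "the latest measurement for that subject up to and including the day of administration of first IMP", unless otherwise stated. Protocol 7.1 says "romosozumab and placebo are considered IMP". SAP 13.8 does not state an ADA-specific alternative.

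**The concern.** A subject randomized to placebo has her first romosozumab dose at Month 6. To call a later positive treatment-emergent, one needs a result from before that dose. Every sample that could supply it (Day 1 to the Month 6 predose draw) comes from the placebo arm, and the SAP says without qualification that placebo samples are not analysed.

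If those samples go unassayed and are handled as missing, category 2 is the only class left for a subject with any later positive. Treating an occasional missing baseline as negative is a usual convention. Here it would apply by design to a whole arm, about a third of the trial.

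At stake are the treatment-emergent incidence in the pooled analysis and in the placebo/romosozumab column, the stated prevalence of pre-existing antibodies, and the displays of BMD change and immune-related TEAEs by ADA class, which inherit the grouping.

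**Working it through.** The plan states no ADA rate, so there is no figure to reproduce. The check traces the rules and then sizes the effect.

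**Step 1: which class is open to a positive subject with no pre-romosozumab result?**
- Category 1 needs all later samples negative.
- Categories 3, 4 and 5 need a positive Baseline.
- Category 6 needs a pre-treatment result, with the available later samples negative.
- Category 2 accepts a missing pre-treatment sample with any later positive. It is the only one that fits.

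**Step 2: what happens under each reading of which samples are assayed?**
- *No pre-romosozumab sample assayed* (plain SAP reading). Every later positive in this arm falls into category 2, and pre-existing reactivity cannot be identified.
- *Month 6 predose sample assayed, Day 1 not* (one way to read the month 6-12 label). SAP 3.3 makes the Month 6 sample post-Baseline, and SAP 3.2.4.3 attributes Month 6 assessments to the double-blind period. A positive found before any romosozumab would then still be a later positive, hence category 2.
- *Day 1 assayed* (one way to read Protocol 11.7.5). Subjects positive on Day 1 move to category 3, 4 or 5, and the excess from unassayed samples disappears. The reference is then six months older than the first romosozumab dose, and the SAP sentence on placebo samples needs correcting.

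**Step 3: size under the first reading.** Inputs from SAP 2.6: 100 placebo and 200 romosozumab subjects planned. Assumptions not in the documents: the pre-existing prevalence p, that all 100 switch, and that pre-existing positives stay positive.

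- Expected number misclassified = 100 × p
- Added to the placebo/romosozumab column = 100 × p / 100
- Added to the pooled rate = 100 × p / 300
- Chance of at least one = 1 − (1 − p)^100

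| Assumed p | Subjects | Column, points | Pooled, points | Chance of at least one |
|---|---|---|---|---|
| 1% | 1 | 1.0 | 0.33 | 0.63 |
| 2% | 2 | 2.0 | 0.67 | 0.87 |
| 5% | 5 | 5.0 | 1.67 | 0.99 |
| 10% | 10 | 10.0 | 3.33 | >0.99 |

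**Step 4: what remains if a pre-romosozumab sample is assayed for everyone.** Only truly missing samples are left, m of 300 subjects. Expected misclassified = 300 × m × p. With assumed m of 1% to 5% and p of 1% to 10%, this runs from 300 × 0.01 × 0.01 = 0.03 to 300 × 0.05 × 0.10 = 1.5 subjects, at most 0.5 pooled points.

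**The case against.** A reader might infer that the plan will certainly report pre-existing antibodies in this arm as caused by romosozumab. The documents do not support that, for these reasons:

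- The SAP does not say that the Day 1 sample, drawn before any IMP, counts as a placebo sample. Protocol 11.7.5 selects by subject, and these women qualify once they switch.
- The missing-sample rule names samples that are absent or too small. It does not name samples collected but left unassayed by design.
- Other text in SAP 13.8 presupposes results in both arms. The Kaplan-Meier display allows for category 5, which needs a positive Baseline, in either treatment group. The BMD-by-ADA figure is to be repeated for placebo too. Some of this may be template text, but it conflicts with the sentence on placebo samples.
- Treatment-induced is a classification label, not a causal finding.

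The reach is also limited. Two of the three planned ADA analyses contain only romosozumab/romosozumab subjects, categories are shown by treatment group, and individual results are listed, so any effect could be separated. The prevalence range is assumption only. The 2% in Protocol 2.2 is neutralizing-antibody incidence in a dose-ranging study of romosozumab and says nothing about pre-existing binding antibodies.

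Finally, taking positives of unknown pre-treatment status out of the numerator would lower reported immunogenicity, the less conservative direction for a safety measure.

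All of this stands, and it makes the misclassification conditional. It does not supply what is missing: no SAP text names a pre-romosozumab ADA reference for the switching arm.

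**Conclusion.** The point holds as a conditional one. On the plain SAP reading, pre-existing reactivity that persists in about 100 of 300 planned subjects would be counted as treatment-emergent; on one reading of Protocol 11.7.5 it would not. The two documents conflict on which placebo-arm samples are assayed, and neither sets the reference that the classification needs.

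The size rests wholly on an assumed prevalence, on full persistence and on all placebo subjects switching: 1 to 10 subjects, or 0.3 to 3.3 pooled points, at 1% to 10%. The effect is confined to descriptive immunogenicity outputs. The primary endpoint, the type I error rate and the sample size are untouched. This is a cheap improvement, not a threat to the trial's conclusions.

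**What to change.** In SAP 13.8:

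1. State that for placebo/romosozumab subjects the Month 6 predose antibody sample, already drawn under Protocol Table 5-1, is assayed and serves as the pre-treatment ADA reference. SAP 3.3 leaves room for such an exception to the general Baseline rule.
2. Reword the sentence on placebo samples so that it agrees with Protocol 11.7.5 and says which placebo-arm samples are assayed.
3. Keep the usual convention for sporadically missing baselines in the main count, and show positives with unknown pre-treatment status on a separate line or as a sensitivity count.

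The cost is SAP wording and up to about 100 assays on samples already scheduled for collection. No visit, blood draw or efficacy analysis changes.
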